3.2 Protocol 1 (Specific Aim 3)

The purpose of this protocol is to validate the CAMCI scoring algorithm on an independent sample of older individuals. Approximately 420 Adult male and female participants 60-95 years of age will be enrolled into this portion of the research study. Prior to enrollment, participants will be screened to determine eligibility for the study.

Baseline

After obtaining informed consent, participants will be asked to complete the MoCA, the CAMCI battery of tasks, a complete paper-pencil neuropsychological test battery, a survey requesting feedback from the participant concerning their experience with the CAMCI application, and a brief reading assessment. The paper-pencil tests will be used by three neuropsychologists (see Appendix A) to adjudicate the participants. The baseline test session will take approximately 2.5 hours to complete, and participants will be paid \$100 for completion of this portion of the study.

If an equivalent and valid neuropsychological task battery assessment (as determined by the project-certified examiner) is available at the time of enrollment in the study, the neuropsychological task battery will not be re-administered, and the protocol will be shortened to administer all remaining elements. In this case, total test session time is estimated to be approximately 60 minutes, and participants will be paid \$50 for completion of the shortened protocol.

Follow-Ups

Participants will be asked to return for two follow-up test sessions at set intervals in relation to their baseline test session (either 6 months and 12 months, or 12 months and 24 months). During the follow-up test sessions, participants will be asked to complete the MoCA, the CAMCI battery of tasks, and a complete paper-pencil neuropsychological test battery (the survey and reading assessment will not be repeated). Each follow-up test session will take approximately 2 hours to complete, and participants will be paid \$75 for each follow-up test session completed. Total compensation for each participant may be up to \$250 for completion of the baseline and 2 follow-up test sessions.

If a participant is unable to complete a test session, or if the experimenter must discontinue a test session before completion, the participant will be paid \$25.

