CAMCI: Advancing the Use of Computerized Screening in Healthcare

Clinical Trial:NCT03512301Secondary ID:NIH: 2SB1AG037357-04A1DATE:Approved by DSMB – July 18, 2019
Uploaded to clinicaltrials.gov - February 14, 2025

Analysis Plan

Validation of CAMCI Algorithm and MoCA with Neuropsychological Adjudication

CAMCI will group participants into three classifications: impaired, non-impaired, and intermediate. Likewise, the neuropsychological adjudication will provide a consensus classification for participants into impaired, non-impaired, and intermediate and thus, CAMCI classifications will be compared to clinical adjudication. Similarly, MoCA classification will be evaluated against the neuropsychological adjudication. MoCA scores are classified as non-impaired (MoCA \geq 26) or impaired (MoCA <17), with intermediate scores occurring between 18-25. To validate the CAMCI and MoCA against the neuropsychological adjudication, we will evaluate positive and negative predictive agreement, accuracy and error bias. Accuracy is defined as the correct identification using CAMCI: ACC=[TP+TN]/total; error bias will be a contrast ratio of false positives and false negatives: FP-FN/FP+FN.

Agreement analysis

Two methods will be used to evaluate the agreement of CAMCI to non-reference (Montreal Cognitive Assessment, MoCA) and reference (clinical adjudication) standards. First, using linear regression, agreement analysis will be done to compare the subject device, CAMCI score (expected to range from 0-50), and the MoCA score (ranging from 0-30). Agreement will be evaluated using the scatterplot, linear regression equation and confidence intervals, and Pearson correlation. It will be expected that each of these evaluation methods will show that those patients who score high on the CAMCI will also score high on the MoCA, indicating agreement between the range of scores that are non-impaired. Likewise, we will expect to see low scores on the CAMCI to be found in those who also show low MoCA scores, indicating agreement in the ranges of impaired scores on both assessments.

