Next, agreement will be assessed using the clinical adjudication categories and the CAMCI classifications. The following table will be used to display the frequencies showing the distribution of patients into the CAMCI classifications (impaired, non-impaired, intermediate/indeterminate) by clinical adjudication (normal, impaired, indeterminate). From this summary, percent agreement (positive and negative), confidence interval estimates, and quadratic weighted kappa will be used to assess the agreement between CAMCI and the reference standard. Finally, this analysis will be repeated with the omission of the intermediate group to show the performance of CAMCI for those who are clearly impaired and clearly non-impaired.

Classification						
TEST		Impaired	Intermediate	Non-impaired		
	Impaired	TP*	FP	FP		
	Intermediate	FN	TP	FP		
	Non-impaired	FN	FN	TN		

Example, Agreement analysis (general case in 3x3):

* TP=True Positive, TN=True Negative, FP=False Positive, FN=False Negative

Example, Agreement analysis (for current study):

Classification by Clinical Adjudication							
CAMCI		Impaired	Intermediate	Non-impaired			
	Impaired	а	b	С			
	Intermediate	d	е	f			
	Non-impaired	g	h	i			

Classification by Clinical Adjudication							
МоСА		Impaired	Intermediate	Non-impaired			
	Impaired	а	b	С			
	Intermediate	d	е	f			
	Non-impaired	g	h	i			

Positive percent agreement (PPA, %) = 100 X (a + e) / (a + b + c + e + f) Negative percent agreement (NPA, %) = 100 X (i) / (d + g + h + i) Accuracy (ACC) = [(a + e) + (i)] / total n Error Symmetry ([(b + c + f) – (d + g + h)] / total n

Change Metric

Test-retest descriptive statistics (mean, standard deviation) will be calculated and compared for the clinical groups (impaired, intermediate, non-impaired). Difference scores will be calculated and analyzed for retest effect and to identify any patterns (improvement/decline) that might differ between the groups on retest. Finally, repeated measures analyses will be used to assess group X retest differences. This information will be used to determine whether adjustments will be made to the reliable change calculations.

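### CAMCI–MoCA correlation and regression measure association; they do not show that the two tests agree in the impaired and non-impaired ranges, and no CAMCI-by-MoCA class table is planned

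*SAP*

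**What the plan says.** The SAP section on agreement analysis sets out two methods. The first compares CAMCI with MoCA, which the SAP calls a non-reference standard. The scores are on different scales (CAMCI expected 0–50, MoCA 0–30), and the listed tools are graphical and linear: "Agreement will be evaluated using the scatterplot, linear regression equation and confidence intervals, and Pearson correlation". No threshold is given for r, the slope, the intercept or the pattern in the plot. The SAP expects high scores to go with high and low with low, and interprets the low end as "indicating agreement in the ranges of impaired scores on both assessments", with a matching statement for the non-impaired range.

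The second method is categorical and uses adjudication as the reference: "quadratic weighted kappa will be used to assess the agreement between CAMCI and the reference standard", alongside positive and negative percent agreement with confidence intervals. MoCA gets a 3x3 table as well, but also against adjudication: "Similarly, MoCA classification will be evaluated against the neuropsychological adjudication".

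Both tests have three classes. For the device, "CAMCI will group participants into three classifications: impaired, non-impaired, and intermediate", with no score cut-offs stated. For MoCA, 26 or more is non-impaired, and the lower ranges are "impaired (MoCA <17), with intermediate scores occurring between 18-25". No table of CAMCI class by MoCA class appears anywhere in the SAP.

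**The concern.** Agreement in the impaired range is a statement about classes: the people one test calls impaired are also called impaired by the other. Whether that is so depends on two things, the scatter around the line and where each test's cut-offs fall. Pearson r and the fitted line describe how the scores move together and take no account of the cut-offs. Moving the CAMCI cut-offs changes who is labelled impaired and leaves r, the slope and the intercept as they were.

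The practical risk lies in reporting. With about 420 participants, a high r will come with a narrow confidence interval, and under the SAP's wording it would be presented as agreement on who is impaired. CAMCI is meant to be a screening tool, and impaired people are the group a screen is meant to find. The SAP already applies a class-based statistic, weighted kappa, to the comparison with adjudication, but uses a score-based one for MoCA and calls both agreement.

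**Working it through.** **No figure to reproduce.** The documents give no expected r, acceptance limit, impaired share or CAMCI cut-off for this comparison. The check therefore asks how far class agreement can vary while r stays fixed.

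**Inputs.**
- From the documents: three classes per test; MoCA classes as quoted; MoCA below 10 excluded (Protocol 4.4); about 420 participants (Protocol 3.2).
- Assumed: bivariate normal scores; on MoCA 15% impaired, 30% intermediate, 55% non-impaired; r = 0.8, varied from 0.6 to 0.9; both CAMCI cut-offs at the matching points, or δ = 0.5 or 1 SD lower.

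**Formula.** In standard units the MoCA cuts are Φ⁻¹(0.15) = −1.036 and Φ⁻¹(0.45) = −0.126, and the CAMCI cuts are these minus δ. The share of MoCA-impaired people whom CAMCI also calls impaired is Φ₂(−1.036, −1.036 − δ; r) / 0.15. Quadratic weighted kappa is 1 − Σw·O / Σw·E, with w = (i − j)²/4, O the joint class proportions and E the product of the margins.

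**Results at r = 0.8.**

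| CAMCI cut-offs | Joint impaired / 0.15 | Matched | CAMCI impaired overall | Weighted kappa |
|---|---|---|---|---|
| aligned | 0.0913 / 0.15 | 61% | 15% | 0.68 |
| 0.5 SD lower | 0.0490 / 0.15 | 33% | 6% | 0.57 |
| 1 SD lower | 0.0191 / 0.15 | 13% | 2% | 0.35 |

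Kappa in the aligned case, as a check: observed weighted disagreement is [2(0.0514) + 2(0.0943)]/4 + 2(0.0073) = 0.0875. Expected is [2(0.15)(0.30) + 2(0.30)(0.55)]/4 + 2(0.15)(0.55) = 0.270. So 1 − 0.0875/0.270 = 0.68.

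In participants, 15% of 420 is 63 MoCA-impaired people, of whom CAMCI would also flag about 38, 21 or 8. The 95% Fisher-z interval for r = 0.8 at n = 420 is 0.76 to 0.83 in all three cases.

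**Sensitivity.** Matched share at r = 0.6, 0.7, 0.8, 0.9:
- aligned: 45, 52, 61, 72%
- 0.5 SD lower: 24, 28, 33, 38%
- 1 SD lower: 10, 11, 13, 14%

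With aligned cut-offs and r = 0.8, an impaired share of 5, 10, 20 or 30% gives 50, 56, 65 or 70%.

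**Limiting case, r = 1.** Suppose CAMCI = 5 + 1.5 × MoCA exactly. MoCA 10 to 16 then maps to CAMCI 20 to 29. A CAMCI cut of below 22 would flag only MoCA 10 and 11 (CAMCI 20 and 21.5), two of the seven impaired score values, despite perfect correlation.

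**Do the two planned tables fill the gap?** In part. The row totals give the number each test calls impaired, so 6% or 2% against 15% would be seen. They do not give the overlap. Suppose, for illustration, that each test calls 60 of 100 adjudicated-impaired people impaired. The number called impaired by both could be anything from 60 + 60 − 100 = 20 up to 60, and the two tables would look the same.

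**The case against.** The strongest reply has four parts.

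1. With scales of 0–50 and 0–30, a score-level association is a reasonable analysis. The expectation is worded directionally, and the planned scatterplot would show departures at the low end. This stands as a defence of doing the analysis. It does not defend the conclusion drawn from it: the scatterplot has no stated criterion and no cut-offs marked.

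2. A large cut-off offset would not stay hidden. A reader might infer that the SAP as a whole could not detect disagreement in the impaired range. That goes too far. The row totals of the two tables against adjudication would reveal it, and the error-symmetry statistic can be computed for each test. Only person-level cross-classification is missing.

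3. A reader might infer that the two tests will in fact classify most impaired people differently. The documents do not support this. They give no r, impaired share or CAMCI cut-offs, and nothing in them suggests an offset. With aligned cut-offs at r = 0.8, 61% match, 34% fall in the adjacent intermediate class and only 5% are called non-impaired.

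4. MoCA is the non-reference comparator and is itself tested against adjudication, so CAMCI–MoCA disagreement is not in itself a device error. This is right, and it limits the weight of the point.

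One technical overreach should also be avoided. A reader might infer that the regression line, like r, is unaffected by shifting or rescaling a score. It is not: the intercept and slope change. What holds is that neither statistic depends on where the class cut-offs lie.

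**Conclusion.** The point holds in a limited form. The inference from correlation and regression to agreement in the impaired and non-impaired ranges does not follow, because the planned statistics ignore the cut-offs that define those ranges. Under the stated assumptions the matched share can run from 61% down to 13%, and weighted kappa from 0.68 to 0.35, at the same r of 0.8. The two lower figures depend on an assumed offset that the documents neither state nor exclude.

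A reader might take this as a flaw in the main validation. It is not: CAMCI against adjudication already has positive and negative percent agreement, confidence intervals and weighted kappa. The point is a correction of wording plus one missing table for the secondary comparator. It is worth making because the data will already be in hand.

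**What to change.** - Describe the correlation and regression as association (convergent validity), and remove the statements that they indicate agreement in the impaired and non-impaired ranges.
- Add a 3x3 table of CAMCI class by MoCA class. Report percent agreement within each class and quadratic weighted kappa, each with a 95% confidence interval, as the CAMCI–MoCA agreement result.
- Before filling that table, assign the MoCA score of 17, which the stated ranges (below 17, 18–25, 26 and above) leave without a class. State the CAMCI cut-offs in the SAP as well.

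The cost is a wording change and one extra table, with no new data. Per-class intervals will be wide if few people are impaired. With 63 MoCA-impaired people and 61% matched, the half-width is about 1.96 × √(0.61 × 0.39 / 63) = 0.12. The reported agreement may also look less favourable than r.

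### The SAP does not say whose intermediate class the repeat agreement analysis omits, and its PPA and NPA do not show how well CAMCI identifies clear cases

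*SAP*

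**What the plan says.** The opening section of the SAP gives both sides of the comparison three levels. For the test: "CAMCI will group participants into three classifications: impaired, non-impaired, and intermediate". For the reference standard: "the neuropsychological adjudication will provide a consensus classification for participants into impaired, non-impaired, and intermediate". The 3x3 table under Agreement analysis therefore has an intermediate row (CAMCI; cells d, e, f) and an intermediate column (adjudication; cells b, e, h). The general version of that table labels d a false negative and f a false positive.

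The full table is analysed first. The section then adds: "this analysis will be repeated with the omission of the intermediate group to show the performance of CAMCI for those who are clearly impaired", and likewise for those clearly non-impaired. It does not name the row or the column, and it gives no reduced formulas.

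The formulas it does give are for the full table:

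- "Positive percent agreement (PPA, %) = 100 X (a + e) / (a + b + c + e + f" (the bracket closes there)
- "Negative percent agreement (NPA, %) = 100 X (i) / (d + g + h + i" (the bracket closes there)
- "Accuracy (ACC) = [(a + e) + (i)] / total n"

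Two other phrases bear on the reading. The paragraph that contains the rule labels the axes as "CAMCI classifications (impaired, non-impaired, intermediate/indeterminate) by clinical adjudication (normal, impaired, indeterminate". The Change Metric section uses the word *groups* for adjudicated status: "compared for the clinical groups (impaired, intermediate, non-impaired".

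**The concern.** The repeat analysis is meant to show how CAMCI performs in people whose status is clear. Status comes from the adjudication, so a CAMCI-intermediate result in such a person is part of CAMCI's performance: an impaired person not called impaired (d), or a non-impaired person not cleared (f). If the intermediate row is dropped as well as the column, these results disappear. The figures then describe only the clear cases that CAMCI classified decisively, and do not show how many it left unresolved. The axis could also be chosen after the results are known.

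A second problem remains however the first is settled. The denominators of positive and negative percent agreement (PPA and NPA) are not the numbers of adjudicated impaired and non-impaired people. They do not give the share of each clear group that CAMCI identifies, which is what the stated purpose calls for.

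**Working it through.** The documents give no expected cell counts, performance target or sample-size derivation for this analysis, so there is no planned figure to reproduce. The formulas and cell labels below are the SAP's. The total of 420 is the approximate enrolment in Protocol section 3.2. All cell counts are assumptions.

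**1. Effect of dropping the CAMCI row as well as the column.** Let N = a+c+d+f+g+i be the number of clear cases and s = (d+f)/N.

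- Column omitted: ACC = (a+i)/N
- Both omitted: ACC = (a+i)/(N−d−f)
- Ratio of the second to the first: N/(N−d−f) = 1/(1−s), which exceeds 1 whenever d+f > 0

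**2. Size over a range of s.** Assume 100 impaired, 100 intermediate and 220 non-impaired people, with 8% of clear cases put in the opposite class. Then ACC is 1−s−0.08 with the column omitted, and (1−s−0.08)/(1−s) with both omitted.

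| s | Factor 1/(1−s) | ACC, column omitted | ACC, both omitted | Gain (points) |
|---|---|---|---|---|
| 2% | 1.02 | 90.0% | 91.8% | 1.8 |
| 5% | 1.05 | 87.0% | 91.6% | 4.6 |
| 10% | 1.11 | 82.0% | 91.1% | 9.1 |
| 20% | 1.25 | 72.0% | 90.0% | 18.0 |
| 30% | 1.43 | 62.0% | 88.6% | 26.6 |
| 40% | 1.67 | 52.0% | 86.7% | 34.7 |

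The opposite-class share changes the levels more than the gain. At s=30%, a share of 2% gives 68.0% against 97.1%, and a share of 10% gives 60.0% against 85.7%.

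**3. Dropping the CAMCI row alone.** Cells b and h now stay in. Take the same assumed table with b=25, e=50, h=25.

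- At s=10%, a=82, c=17.6, f=22, g=8, i=180.4. With the row omitted, ACC = 262.4/338 = 77.6%, below the 82.0% with the column omitted. PPA = 82/124.6 = 65.8%, against 82/121.6 = 67.4%.
- At s=20%, a=72 and i=158.4. With the row omitted, ACC = 230.4/306 = 75.3%, against 72.0%.

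The overall figures can therefore move either way.

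**4. What PPA and NPA become when only the adjudicated-intermediate column is omitted.** Setting b=e=h=0 gives PPA = a/(a+c+f) and NPA = i/(d+g+i). Take a second assumed table of 420: a=40, d=20, g=3; c=5, f=45, i=197; b=25, e=70, h=15. Here s = 65/310 = 21%.

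| Quantity | Column omitted | Both omitted |
|---|---|---|
| Impaired identified, a/(a+d+g) | 40/63 = 63% | 40/43 = 93% |
| Non-impaired identified, i/(c+f+i) | 197/247 = 80% | 197/202 = 98% |
| SAP PPA | 40/90 = 44% | 40/45 = 89% |
| SAP NPA | 197/220 = 90% | 197/200 = 98.5% |
| SAP ACC | 237/310 = 76.5% | 237/245 = 96.7% |

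With the column omitted, PPA puts f (adjudicated non-impaired) in its denominator and leaves out d and g (adjudicated impaired). NPA does the reverse. Neither is a rate within an adjudicated class. Here PPA falls below the share of impaired people identified (44% against 63%), and NPA lies above the share of non-impaired people identified (90% against 80%).

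**The case against.** The strongest reply is that the sentence explains itself. Its purpose clause describes people by true status, the Change Metric section uses *groups* for adjudicated categories, and the section mostly calls CAMCI outputs classifications. On that reading only the column goes, and d and f stay. This is the more natural reading, and a reader who infers that the SAP plans to discard CAMCI's errors goes further than the text. The wording still does not settle the matter: the SAP also says that CAMCI groups participants, and the paragraph with the rule uses the word *intermediate* for CAMCI while calling the adjudicated middle class indeterminate.

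A second reply is that the full 3x3 table is planned and keeps d and f. If all nine cells are shown, any version can be recomputed. That stands, and it limits the harm. It does not fix in advance which version is reported as clear-case performance.

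A third reply is that the row-type denominators may be deliberate, since the opening section speaks of predictive agreement. With the column omitted, however, f is in the PPA denominator although CAMCI did not call those people impaired, so PPA is not a plain predictive value either. Accuracy does remain a valid overall clear-case figure, but it does not separate impaired from non-impaired people.

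Four further inferences are tempting and not supported:

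- That the inflation must be large. It depends on s, which the documents do not give.
- That only misses would be removed. Cell f holds over-calls, and the outright misses in g remain.
- That dropping the CAMCI row alone must raise the SAP's overall accuracy or PPA. The third step of the working shows that it need not.
- That this will be the most quoted result. The SAP names no headline measure for this analysis.

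**Conclusion.** The concern holds as an undefined rule with a second, related defect. The SAP leaves open whether adjudicated-intermediate participants, CAMCI-intermediate results or both are omitted. If both are, clear-case accuracy is multiplied by exactly 1/(1−s). That result is algebra and rests on no assumed counts. Its size in points does: about 2 at s=2%, 9 at 10%, 18 at 20% and 27 at 30%, with 8% of clear cases assumed to fall in the opposite class.

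Separately, even on the natural reading, the SAP's PPA and NPA do not measure performance among clearly impaired and clearly non-impaired people. The reduced formulas show this directly; the contrast of 44% and 90% with 63% and 80% illustrates it in one assumed table.

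The rule should be settled in the SAP. The purpose clause and the planned full table keep the point from being graver.

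**What to change.** In the Agreement analysis section of the SAP:

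- State that only participants adjudicated intermediate are omitted.
- Keep CAMCI-intermediate results of clear cases in the denominator, counted as non-agreement.
- For this analysis, report a/(a+d+g) and i/(c+f+i) with confidence intervals.
- Beside them, report the number and share of clear cases that CAMCI calls intermediate, (d+f)/(a+c+d+f+g+i).
- Apply the same rule to the MoCA table.
- Label any version that also drops test-intermediate results as supplementary.

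If the analysis has already been run, state which cells were left out and report the version described here.

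The cost is a few sentences and two formulas, with no new data. The downside is that the clear-case figures may be less favourable than in a 2x2 analysis that drops both classes.

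### The SAP's positive and negative percent agreement formulas are TP/(TP+FP) and TN/(TN+FN), and no rate conditional on the adjudicated category is pre-specified

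*SAP*

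**What the plan says.** The first section of the SAP (Validation of CAMCI Algorithm and MoCA with Neuropsychological Adjudication) announces the measures: "we will evaluate positive and negative predictive agreement, accuracy and error bias". It defines the last of these as follows: "error bias will be a contrast ratio of false positives and false negatives: FP-FN/FP+FN".

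The Agreement analysis section cross-tabulates the test (CAMCI, and in a second table MoCA) in rows against clinical adjudication in columns, with cells a to i read row by row. A general version of the table marks each cell ("TP=True Positive, TN=True Negative, FP=False Positive, FN=False Negative"): a and e are TP; b, c and f are FP; d, g and h are FN; i is TN. Percent agreement, its confidence intervals and quadratic weighted kappa "will be used to assess the agreement between CAMCI and the reference standard". The formulas are:

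- "Positive percent agreement (PPA, %) = 100 X (a + e) / (a + b + c + e + f)"
- "Negative percent agreement (NPA, %) = 100 X (i) / (d + g + h + i)"
- accuracy: (a+e+i) over total n
- "Error Symmetry ([(b + c + f) – (d + g + h)] / total n"

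The section also states that "this analysis will be repeated with the omission of the intermediate group". It gives no separate formulas for that repeat.

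**The concern.** A figure presented as percent agreement with a reference standard should say how often the test is right among people whom the reference places in a given category. Its denominator should be a column of this table. The printed denominators are built mainly from rows. As a result, under-called participants (d, g, h) appear nowhere in PPA and over-called participants (b, c, f) appear nowhere in NPA. Both figures also depend on how many impaired, intermediate and non-impaired people happen to be enrolled.

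Protocol section 3.2 exists to validate the CAMCI scoring algorithm. For a screening tool, a basic question is what share of adjudicated impaired people it detects, and no planned measure answers it. Protocol section 3.3 asks whether the algorithm carries over to other populations. PPA and NPA could differ between the two samples through case mix alone. That is only a possibility, since neither case mix is given and the SAP specifies no such comparison.

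Two smaller gaps sit in the same block. The repeat analysis does not say by which classification the intermediate group is dropped. The fourth measure has two names and two denominators.

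**Working it through.** The documents state no numerical PPA or NPA, so there is no figure to reproduce. The check has an exact part and an illustrative part.

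**Exact part.** Put the SAP's labels into its formulas.

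- PPA = (a+e)/(a+b+c+e+f) = (a+e)/[(a+e)+(b+c+f)] = TP/(TP+FP)
- NPA = i/(d+g+h+i) = TN/(TN+FN)

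These are not clean row-wise predictive values either. Cell d (CAMCI intermediate, adjudicated impaired) is in the NPA denominator, while e and f from the same row are in the PPA denominator. Accuracy, both error measures and kappa do not have an adjudicated-category denominator.

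**Illustration.** All rates and case mixes are assumed. n=420 is the approximate Protocol 1 enrolment. The assumed chances of being called impaired/intermediate/non-impaired are .80/.15/.05 for adjudicated impaired, .15/.65/.20 for intermediate and .03/.17/.80 for non-impaired.

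At a mix of 30/60/330 (impaired/intermediate/non-impaired) the expected cells are a=24, b=9, c=9.9; d=4.5, e=39, f=56.1; g=1.5, h=12, i=264. So TP=63, FP=75, FN=18 and TN=264.

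- Written PPA = 63/138 = 45.7%; written NPA = 264/282 = 93.6%
- By column: 24/30 = 80.0%, 39/60 = 65.0%, 264/330 = 80.0%
- PPA pooled over the impaired and intermediate columns: 63/90 = 70.0%

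*Same device, different mix:*

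| Mix | Written PPA | Written NPA | Column rates |
|---|---|---|---|
| 30/60/330 | 45.7% | 93.6% | 80.0/65.0/80.0% |
| 60/90/270 | 106.5/174 = 61.2% | 216/246 = 87.8% | 80.0/65.0/80.0% |
| 140/140/140 | 203/252 = 80.6% | 112/168 = 66.7% | 80.0/65.0/80.0% |

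*Worse device at 30/60/330:* change only the impaired column to .40/.30/.30, so a=12, d=9, g=9. Detection of impaired falls from 80.0% to 40.0%. The like-for-like pooled column value falls from 70.0% to 51/90 = 56.7%. Written PPA falls only from 45.7% to 51/126 = 40.5%, and written NPA from 93.6% to 264/294 = 89.8%. Kappa falls from 0.63 to 0.48.

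*Limiting table:* a=1, g=29, h=60, i=330, all other cells 0. Written PPA = 1/1 = 100%, although 89 of the 90 impaired or intermediate participants are missed. The other measures show the failure: NPA and accuracy are 78.8%, Error Symmetry is -89/420 = -0.21 and kappa is 0.04.

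*Repeat analysis at 30/60/330:* if only adjudicated intermediates are dropped, column agreement for impaired and non-impaired is 80.0% and 80.0%. If CAMCI intermediates are dropped too, it is 24/25.5 = 94.1% and 264/273.9 = 96.4%. In that second case the SAP's formulas reduce to a/(a+c) and i/(g+i), which still condition on the test result.

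*Fourth measure at 30/60/330:* (75-18)/(75+18) = 0.61 by the first section, read with the brackets it lacks, and (75-18)/420 = 0.14 by the Agreement analysis section.

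**The case against.** The strongest reply is that the first section of the SAP speaks of predictive agreement, and TP/(TP+FP) and TN/(TN+FN) are predictive-type ratios. On that reading only the later label is wrong, and leaving misses out of PPA is simply what a predictive value does. This is a fair account of how the formulas may have arisen, but it does not rescue the plan. The Agreement analysis section still reports these ratios as agreement with the reference standard, the position of cell d keeps them from being true predictive values, and no column rate is defined under any name.

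Second, the 3x3 counts will be shown, so anyone can derive column rates. Misses also enter NPA, accuracy, Error Symmetry and kappa, and no success threshold rests on PPA or NPA. All of this stands and limits the harm. Rates derived after the results are seen are still not pre-specified.

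Third, the written formulas need not flatter the device. At 30/60/330 the written PPA of 45.7% is below the pooled column value of 70.0%, so correction would raise PPA and lower NPA from 93.6% to 80.0%. That is right: the direction of the error depends on case mix. The limiting table is contrived, and the 80%-to-40% contrast is fairer when set as 70.0% to 56.7% against 45.7% to 40.5%.

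On the side issues, dropping intermediates by adjudication is the more natural reading, and the two error measures may be meant as separate. The SAP says neither explicitly.

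**Conclusion.** The concern holds. That the printed PPA and NPA are TP/(TP+FP) and TN/(TN+FN), and that no adjudicated-category rate is pre-specified, follows from the SAP's own table and labels without any assumption. It affects CAMCI and MoCA alike. The size depends on assumed rates and mixes: with column performance held at 80/65/80%, the written PPA moves by about 35 points (45.7% to 80.6%) and the NPA by about 27 points (93.6% to 66.7%). The error could make the tool look better or worse than it is. It would not be fully hidden, given the other planned summaries, but the named agreement measures are wrong as written and must be corrected.

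**What to change.** For both CAMCI and MoCA, define agreement by adjudicated column, each with a confidence interval:

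- impaired: a/(a+d+g)
- intermediate: e/(b+e+h)
- non-impaired (NPA): i/(c+f+i)

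If a single pooled PPA is wanted, use (a+e)/(a+b+d+e+g+h) or a pre-specified dichotomy. State that the pooled value still depends on the split between impaired and intermediate: with the assumed device it is 66.7% at 10/80/330 and 78.3% at 80/10/330.

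If predictive values are wanted, report them under that name with row denominators: (a+e)/(a+b+c+d+e+f) and i/(g+h+i).

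For the repeat analysis, use column denominators as well. State whether intermediates are omitted by adjudication only, with CAMCI-intermediate results kept in the denominators, or by both classifications.

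Give the error measure one bracketed definition in both sections, or name two separate measures.

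The cost is SAP wording and a few lines of code, with no new data. Some reported percentages will fall and others may rise.
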